## 3.2 Ethical conduct of the study

The study will be performed in accordance with ethical principles that have their origin in the Declaration of Helsinki and are consistent with ISO 14155 and applicable regulatory requirements.

Dentsply Sirona Implants and the Investigator are obliged to take over the responsibilities specified for both roles in the current ISO 14155.

### 3.3 Informed consent

The Informed Consent Form (ICF) must be approved by the responsible IEC/IRB prior to the study start.

The PI will ensure that the subject is given full and adequate oral and written information about the nature, purpose, possible risk and benefit of the study. The PI is responsible for ensuring that consent is given freely. Subjects must also be notified that they are free to discontinue from the study at any time. The subject should be given the opportunity to ask questions and sufficient time to consider the information provided. The subject's signed and dated informed consent must be obtained before any study specific procedure is performed.

The PI must store the original, signed ICF in the Investigator Site File (ISF). A copy of the signed ICF must be given to the subject.

If modifications are made according to local requirements, the new version has to be approved by Dentsply Sirona Implants and by the responsible IEC/IRB.

# 3.4 Subject data protection

The ICF will incorporate wording that complies with relevant data protection and privacy legislation. Pursuant to this wording, subjects will authorize the collection, use and disclosure of their study data by the Investigator and by those persons who need that information for the purposes of the study.

The ICF will explain that study data will be stored in a database, maintaining confidentiality in accordance with national data legislation. All data stored in the study data base and/or processed by the data manager and Dentsply Sirona Implants will be 'pseudonymized' and is identified by the study code and the subject identification number. The ICF will also explain that for data verification purposes, authorized representatives of Dentsply Sirona Implants, a regulatory authority and/or an IEC/IRB may require direct access to parts of the hospital or practice records relevant to the study, including subject's medical history. The only information revealing the connection between subjects' real identity and study subject number will be stored securely at the respective study site.

### 3.5 Insurance

Subjects participating in this clinical study are insured by Dentsply Sirona Implants, provided that the CIP and other written procedures are followed. For further details, see the CSA.

# 4 Study design

# 4.1 Overall study design

A prospective, non-controlled, multicentre study on the Acuris-conometric concept. The study comprises a 5 year follow-up from baseline, permanent restoration, and includes 11 visits. Each subject will receive one single implant placed in position 17-27 or 37-47 to support a single restoration. The implant will be placed in fresh extraction socket or healed ridge using one- or two-stage surgical protocol, immediate or conventional loading. The permanent restoration must be in place within six months after implant surgery at the latest. A conometric abutment will be used for the prosthetic restoration. The final crown will be cemented onto the final cap extraorally and fixated on the conometric abutment using retention mode.

The sample size estimation shows that 133 fully evaluable subjects are needed to fulfill the primary objective. Given an assumed drop-out rate of 15 % the aim is to include 157 subjects in total, see section 10.4 "Determination of sample size" for details.

However, if the drop-out rate is lower or higher than the estimated level, the number of enrolled subjects may be adjusted in order to reach the 133 fully evaluable subjects.

It is expected that the study will include 9 study sites and that each study site will enroll approximately 15-20 subjects using the Acuris-conometric concept on the implant systems; Ankylos, Astra Tech Implant System or Xive. Each site will use only one implant system.

The overall study design is presented in Appendix B: Visit and procedure plan.

## 4.1.1 Study duration

Anticipated FSI: 2019 May Anticipated LSI: 2020 August Anticipated LSO: 2025 September Anticipated DBL: 2026 February

# 4.2 Choice of outcome variables and study population

### 4.2.1 Choice of outcome variable

Prosthetic survival is chosen as primary objective to show that the Acuris-conometric concept has performed according to expectations during the study, since this is a new mode of retention using friction for seating the crown of single tooth restorations without using cement or screws.

### 4.2.2 Choice of study population

Subjects in need of single tooth replacement have been chosen, since this is the target subject population for treatment with the Acuris-conometric concept.

# 5 Study procedures

### 5.1 Visits

The pseudonymized subject data, investigation results and procedures during the treatment phase as well as safety information will be documented in the Electronic Case Report Form (eCRF) during the study.

The table in Appendix B: Visit and procedure plan shows an overview of all study specific visits and procedures.

Additional visits may be scheduled at the discretion of the investigator recorded as extra visits in the eCRF.

The Fédéderation Dentaire Internationale (F.D.I.) will be used, see Appendix C: Dental chart.

*Pre-screening activity (outside study)* – Investigator or delegate may identify potentially suitable study subjects by e.g. a database search, when seeing patients at regular dental appointments at the clinic or evaluating referrals. If possible, an unbiased discussion on available treatment options, and an initial review of certain predefined selection criteria could be performed.

Throughout the study, the guidelines in the following manuals should be followed:

- Surgical manual Ankylos (32671086-USX-1804)
- Surgical manual Astra Tech Implant System (32671181-USX-1804)
- Surgical manual Xive (32670050-USX-1810)
- Acuris-conometric concept, Manual and product catalog Ankylos (32671509-USX-1808)
- Acuris-conometric concept, Manual and product catalog Astra Tech Implant System (32671510-USX-1810)
- Acuris-conometric concept, Manual and product catalog Xive (32671511-USX-1812)
- Clinical Photography Manual (32671374-USX-1708)

Clinical photographs should be taken for at least 5 subjects selected by each study site. Clinical photographs can be used in future case presentations, scientific publications etc.

Radiographs and clinical photographs obtained during the study will be uploaded into the eCRF by the Investigator.

# 5.1.1 Visit 1 Screening and pre-surgical planning

Subjects in need of a single implant restoration will be screened and considered for treatment in the study. Only one implant per subject will be included within the study. Subjects fulfilling all of the Inclusion criteria and none of the Exclusion criteria, are considered eligible for participating

in the study. Clinical photographs will be taken (at least 5 subjects).

#### 5.1.1.1 Written informed consent

If the subject is eligible, the subject will be informed orally and in writing about the study, and must have signed the ICF before any study specific procedures are performed (see section 3.3 Informed consent).

#### 5.1.1.2 Pre-operative planning

Treatment considerations for implant subjects should include an evaluation of:

- Oral health status (incl. periodontal status and restorative status)
- Medical status (anamnesis)
- Risk factors

During pre-operative planning it is important to check that the height and width of the jawbone is sufficient for placement of the implant. Bone quality and quantity, expected primary implant stability, design of restoration and loading conditions should always be carefully examined and assessed by the clinician when determining time to loading of the implant.

The screening procedure will include collection of demographic data, see section 6.2 "Demographics and other baseline characteristics". Pre-surgical planning should follow the guidelines described in applicable surgical manual. This procedure will include a clinical and radiographical examination, e.g. panoramic, intra-oral or Cone Beam Computed Tomography (CBCT). Pre-existing radiographs deemed by the investigator as being insufficient to assess subject eligibility or being older than six months, will prompt a new radiographic examination.

### 5.1.2 Visit 2 Implant Placement (IP)

Subjects meeting all of the inclusion and none of the exclusion criteria will be treated according to the study protocol. Subjects not fulfilling the criteria will be terminated from the study and will receive an appropriate treatment and thereafter followed according to the clinic's standard practice. The subject will receive antibiotic prophylaxis according to local practice and a prescription for post-surgical chlorhexidine rinse (twice daily for 10 days). Other pre-surgical, surgical and post-surgical care will be given at the discretion of the investigator and recorded in appropriate sections in the eCRF.

Pre-surgical radiographic findings of bone quality and quantity (Lekholm and Zarb) from visit 1, will be determined during surgery and recorded in eCRF. Primary implant stability will be examined manually by the investigator and recorded as "Yes/No" in the eCRF. If needed, minor grafting and soft tissue grafting may be performed. Intraoral radiographs will be obtained. Clinical photographs will be taken (at least 5 subjects). All types of safety events (6.4.1 Types of safety events) will be recorded.

Each study site will use their assigned implant system; Ankylos, Astra Tech Implant System or Xive, and must follow the guidelines described in applicable manuals(a-f).

The implant can be placed in a healed ridge or in a fresh extraction socket.

During the surgery, based on the quality of supporting bone and the initial stability of the implant, the investigator will determine the final treatment approach, i.e.:

- One- or two-stage surgical procedure
- Immediate or conventional loading protocol

Prepare the implant site and install the implant. At implant installation, decide one of the following approaches:

- 1. The use of cover screw
- 2. The use of healing abutment/gingiva former

- 3. The use of Conometric Abutment, Conometric Temporization Cap and Temporary crown (immediate temporization)
- 4. The use of Conometric Abutment and Conometric Healing Cap

Applicable for choice 3 and 4:

- Measure the soft tissue height. It is preferable to place the abutment margin 1 mm below he soft tissue margin. Select the appropriate conometric abutment with regard to height and angulation. Use applicable instruments for the installation and assure tightening at recommended torque for each implant brand.
- Make sure to record the reference number and lot number of the conometric abutment in eCRF for each subject, mark the package with applicable subject ID and keep at the clinic.
- When immediate loading is selected, the Conometric Temporization Cap is used for temporary restoration. It is important to avoid interference from the mucosa surrounding the abutment. Ensure sufficient space for the final restoration by designing the temporary crown in a way that allow the mucosa to heal in a suitable shape.
- When a temporary crown is not needed an alternative is to use a Conometric Healing Cap which will be snapped onto the abutment.
- a) Surgical manual Ankylos (32671086-USX-1804)
- b) Surgical manual Astra Tech Implant System (32671181-USX-1804)
- c) Surgical manual Xive (32670050-USX-1810)
- d) Acuris-conometric concept, Manual and product catalog Ankylos (32671509-USX-1808)
- e) Acuris-conometric concept, Manual and product catalog Astra Tech Implant System (32671510-USX-1810)
- f) Acuris-conometric concept, Manual and product catalog Xive (32671511-USX-1812)

### 5.1.3 Visit 3 (IP + 1-2 weeks)

One to two weeks after implant placement the subject will return for clinical examination of the implant/abutment and the healing process. Any sutures will be removed and the subject will be given oral hygiene instructions. All types of safety events will be recorded.

### 5.1.4 Visit 4 Impression (IP + max 5 ½ months)

The subject will return to the clinic for impression taking no later than  $5 \frac{1}{2}$  months after surgery, depending of the loading protocol.

**NB:** Schedule the impression visit so that the final crown can be produced and delivered within 6 months after implant placement.

Implant stability will be examined manually. If no pain or mobility is present, impressions will be taken for fabrication of the final crown.

The impression will be made on conometric abutment level, following the guidelines described in applicable Acuris-conometric concept Manual and product catalogd-f.

- If a healing abutment/gingiva former or a cover screw was placed, unscrew and install the appropriate Conometric abutment before the impression taking.
- If a Conometric Temporary Crown or a Conometric Healing Cap is in place, remove these before impression taking.
- Align the Conometric Impression Cap with the indexing part of the abutment and seat it firmly, allowing it to snap into place.
- Take the impression using a closed tray impression technique.
- Reinstall the Conometric Temporary Crown or reinstall/install the Conometric Healing Cap.
- Send the impression together with a Conometric Final Cap to the laboratory for fabrication of the final crown. Before sending the package, record the reference and lot number of the Conometric Final Cap in eCRF and mark the package with applicable subject ID.
- Lab produces the final ceramic crown (all ceramic; e.g. lithium disilicate, Zirconia), using the Conometric Analog and the Conometric Lab Cap, and cements the final crown onto the

Conometric Final Cap.

- Lab sends the final crown, together with the empty package, to the clinic.
- The package must be stored at the clinic in order to track the Investigational Product.

Clinical photographs will be taken (at least 5 subjects). All types of safety events will be recorded.

### 5.1.5 Visit 5 Permanent Restoration (PR) (IP + max 6 months)

The permanent restoration must be in place within six months after implant placement, following the procedures described in Acuris-conometric concept Manual and product catalogd-f. Implant stability will be examined manually. A clinical examination evaluating the periimplant mucosa (Probing Pocket Depth (PPD) and Bleeding on Probing (BoP)) will be performed. Oral hygiene instruction will be given if needed. Intraoral radiographs will be obtained. Clinical photographs will be taken (at least 5 subjects). All types of safety events will be recorded.

- Remove the Conometric Temporary Crown or Conometric Healing Cap.
- Select a suitable single-use tip and attach to the Conometric Fixation Tool depending on the crown form.
- Place the final crown aligned with the index on the abutment.
- Check occlusion and contact points.
- If needed, remove the crown for correction and polishing, and then reinsert the crown aligned with the index on the abutment.
- Press the Conometric Fixation Tool towards the crown to activate the friction retention between Conometric Final Cap/final crown and abutment. An audible click occurs when the spring is released and activates the retention.
- Check retention manually.

# 5.1.6 Visit 6-11 Follow-up (PR + 6 months, 1, 2, 3, 4, 5 years) (± 1 month)

The subject will return for follow-up visits at 6 months, 1, 2, 3, 4 and 5 years after permanent restoration. At all follow-up visits a clinical examination evaluating the presence of plaque and the condition of periimplant mucosa (PPD and BoP) will be performed. Plaque will be recorded as presence of plaque by visual inspection on four surfaces at each implant site. If a high presence of plaque is noted the subject should be re-instructed concerning oral hygiene. Intraoral radiographs will be taken at 1, 3 and 5 year follow-up visits. Clinical photographs will be taken at 1, 3 and 5 year follow-up visits (at least 5 subjects). All types of safety events will be recorded at all follow-up visits.

## 5.2 Compliance

Subjects will be asked to return to all visits and to follow the Investigator's instructions regarding the treatment at any time (post-surgery activities etc.). Non-compliance is defined as subjects obviously disregarding the Investigator's instructions. Subjects judged to be non-compliant may continue in the study for safety reasons, but the reimbursement of the treatment will be reduced as described in the CSA.

# 5.3 Study population

Subjects, aged between 18-75 years, in need of single tooth replacement will be screened and considered for implant treatment in the study. Only one implant per subject will be included within the study.

### 5.3.1 Selection records

The Investigator(s) must keep a Screening Log of subjects who were considered for enrollment. Subjects listed on the log are either enrolled or failed to fulfill inclusion-/exclusion criteria, so called 'Screening failures'.

This information is necessary to establish to assure the subject population was selected without bias.

#### 5.3.2 Identification records

The Investigator(s) must also keep and maintain a Subject Identification Log with e. g. full name, date of birth, subject id etc. of all subjects who have been enrolled and treated within the scope of the study. This information is necessary to be able to identify the participating subjects.

The Subject Identification Log remains on site and will not be collected or copied by Dentsply Sirona Implants.

### 5.3.3 Subject-selection criteria

#### 5.3.3.1 Inclusion criteria

For inclusion in the study subjects must meet all of the following criteria:

- 1. Subject aged between 18-75 years
- 2. Subject signed and dated the informed consent form
- 3. In need of an implant replacing a missing tooth in position 17 to 27 or 37 to 47, and each subject can only receive one study implant.
- 4. Neighbouring tooth to the planned implant must have
  - a natural root or an implant supported restoration mesially
  - a natural root or an implant supported restoration distally

Exemption: If the planned implant is in the second molar position, an edentulous space is accepted distally.

- 5. Presence of natural tooth, partial prosthesis and/or implant supported restoration in the opposite jaw in contact with the planned crown
- 6. Deemed by the investigator as likely to present an initially stable implant situation

#### 5.3.3.2 Exclusion criteria

Any of the following is regarded as a criterion for exclusion from the study (all criteria applies at study inclusion, but criteria numbered 1-5 also applies during the entire study period):

- 1. Unlikely to be able to comply with study procedures, according to Investigators judgement
- 2. Subject is not willing to participate in the study or not able to understand the content of the study
- 3. Involvement in the planning and conduct of the study
- 4. Severe non-compliance to CIP as judged by the Investigator and/or Dentsply Sirona Implants.
- 5. Unable or unwilling to return for follow-up visits for a period of five years
- 6. Simultaneous participation in another clinical study, or former participation in a clinical study during the last 6 months that may interfere with the present study
- 7. Previous enrolment in the present study
- 8. Uncontrolled pathological process in the oral cavity
- 9. Known or suspected current malignancy
- 10. History of radiation therapy in the head and neck region within 12 months prior to surgery
- 11. Systemic or local disease or condition that could compromise post-operative healing and/or osseointegration
- 12. Uncontrolled diabetes mellitus

- 13. Corticosteroids, iv bisphosphonates or any other medication that could influence postoperative healing and/or osseointegration
- 14. Current need for major bone grafting and/or augmentation in the planned implant area (minor grafting and soft tissue grafting are allowed)
- 15. Present alcohol and drug abuse
- 16. Smoking more than 10 cigarettes per day

#### **Exclusion criteria at Visit 5 (Permanent Restoration)**

17. Permanent restoration delivered later than 6 months after implant placement

### 5.4 Restrictions

To avoid excessive loading of the implant during the healing period the subject should be informed to avoid food difficult to chew from implant placement to delivery of permanent prosthetic restoration according to the dentist judgement.

If the subject is a smoker, smoking should be limited to a maximum of 10 cigarettes per day.

# 5.5 Discontinuation of subjects from study

### 5.5.1 Criteria for discontinuation

Subjects may be discontinued from the study at any time. Specific reasons for discontinuing a subject may include:

- Voluntary discontinuation by the subject who is free to at any time discontinue his/her participation in the study, without prejudice to further treatment.
- Safety reasons as judged by the Investigator or Dentsply Sirona Implants.
- Severe non-compliance to the CIP as judged by the Investigator and/or Dentsply Sirona Implants.
- Incorrect enrollment, i.e. a subject did not to meet the required inclusion/exclusion criteria for the study, but nevertheless was enrolled (see section 5.3.3 Subject-selection criteria).
- Subject lost to follow-up (as defined by the inability to reach the subject after 3 attempts to contact him/her e.g. by phone, e-mail or letter; all should be documented in the subject's medical records).
- Loss of the study implant. (If a new implant is placed, the new implant should not be recorded in the eCRF.)
- Subjects in need of replacement of existing Investigational Product (IP) (abutment or final cap) after Permanent Restoration (PR).
  - Removal of existing IP after PR for adjustments (e.g. maintenance, polish, esthetic adjustments of crown) is not reason for discontinuation.
  - A loose abutment screw, is not reason for discontinuation if replacement of the abutment screw is possible without changing the abutment.

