## 2.2 Secondary objectives

Secondary objectives	Corresponding secondary outcome variables
Evaluate prosthetic survival 3 and 5 years after permanent restoration	Prosthetic survival will be categorized as No/Yes (see Primary objective)
Evaluate implant survival rate up to 5 years after permanent restoration.	Implant survival will be evaluated clinically and radiographically
Evaluate maintenance of marginal bone levels up to 5 years after permanent restoration.	Marginal Bone Levels and alterations
Evaluate condition of the peri- implant mucosa up to 5 years after permanent restoration.	Bleeding on Probing, Probing Pocket Depth and Plaque

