### 6.3.1.2 Assessment of primary outcome variable

Prosthetic survival will be categorized as No/Yes.

It will be categorized as 'Yes' if all of the following criteria is fulfilled:

- permanent restoration is remaining in situ
- no loss of conometric retention between abutment and final cap
- no fracture of abutment
- no loss of abutment

It will be categorized as 'No' if any of the following is fulfilled:

- permanent restoration not in situ
- loss of conometric retention between abutment and final cap
- fracture of abutment
- loss of abutment

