#### 6.3.2.2 Implant survival

Implant survival rate up to five years after permanent restoration (number of implants in situ). Any implant that is removed or lost after permanent restoration will be considered an implant loss, whatever the reason for removal.

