### 10.3.2 Secondary objectives

Prosthetic survival 3 and 5 years after permanent restoration.

Analysis equivalent to primary objective will be performed.

Evaluate implant survival rate up to 5 years after permanent restoration.

Proportion of survived implants will be calculated.

A two sided exact binomial 95% confidence interval for the proportion of lost implants will be calculated.

Marginal bone levels alteration up to 5 years after permanent restoration

The measured aspects/sides as well as implants mean value will be presented and used in analysis. Descriptive statistics for absolute values and the change from baseline (Visit 5; Permanent Restoration) will be calculated, in addition the marginal bone level change from implant placement may be calculated. Analysis of the change over time using the Wilcoxon Signed Rank test will be included

Condition of the peri-implant mucosa.

Descriptive statistics will be presented and analysis over time will be included.

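### After an abutment or cap replacement, implant status and new adverse events can go unobserved, and no analysis rule covers these subjects

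*Combined protocol and SAP*

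**What the plan says.** Section 5.5.1 opens its list with "Specific reasons for discontinuing a subject may include" and then includes "Subjects in need of replacement of existing Investigational Product (IP) (abutment or final cap) after Permanent Restoration (PR". Two exceptions follow: "Removal of existing IP after PR for adjustments (e.g. maintenance, polish, esthetic adjustments of crown) is not reason for discontinuation" and "A loose abutment screw, is not reason for discontinuation if replacement of the abutment screw is possible without changing the abutment". The exceptions show that the item is meant to be applied in practice.

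Section 5.5.2 sets out what happens at discontinuation. The subject is asked for the reason and about safety issues, is examined if possible, and a termination form is completed. Safety events are followed up, and further care passes to local practice. It mentions no later study visit, check of implant status or collection of new events.

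The outcomes run longer than that. Section 2.2 has the objective "Evaluate implant survival rate up to 5 years after permanent restoration", and section 6.3.2.2 adds "Any implant that is removed or lost after permanent restoration will be considered an implant loss, whatever the reason for removal". The analysis in section 10.3.2 is "Proportion of survived implants will be calculated", with an exact 95% confidence interval for the proportion lost. Section 2.3 collects adverse events at every visit, and section 10.2 reports them from delivery of the restoration to the end of the study.

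Section 10.1.3 refers the analysis of dropouts to section 10.2. Section 10.2 defines the analysis sets but gives no denominator or censoring rule for subjects who leave.

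**The concern.** The implant can be sound and in place when the abutment or cap on it is replaced. If the subject then leaves, the plan still promises a five-year implant outcome and safety reporting to the end of the study, but collects neither from that date. The exit is triggered by the device under study, so it cannot be presumed unrelated to what happens to the implant later. Section 1.3 itself allows that the new retention mode may bring technical and biological complications in the short or long term. Biological events that follow a technical failure are among those lost.

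Other rules in the plan lean towards retention. Section 5.2 lets non-compliant subjects stay in for safety reasons, and section 5.5.3 keeps subjects who received the product despite an eligibility violation.

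At stake are a secondary estimate with few expected losses, where a handful of unknown implants matters, and the record of new events after a device failure.

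**Working it through.** **Inputs from section 10.4.** Five-year prosthetic survival from the literature is 96.3% (95% CI 94.2-97.6%), so 3.7% fail (2.4-5.8%). Assumed one-year survival is 97% and the tested limit 90%. There are 133 evaluable and 157 enrolled subjects, with 15% dropout.

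**Assumptions not in the documents.** Implant loss of 3% in retained subjects and q = 3% to 20% after replacement; every prosthetic failure leads to replacement and exit (an upper case); exits fall evenly over five years; those who exit are left out of the denominator.

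1. *The plan's own figures.* n = [(1.9600 × √(0.90 × 0.10) + 1.2816 × √(0.97 × 0.03)) / 0.07]² = 132.8, hence 133. Then 133 / 0.85 = 156.5, hence 157. Both reproduce, and nothing below changes them. The plan gives no figure for exits through replacement or for expected implant survival.

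2. *Subjects leaving by year 5.*
   - Of 157: 157 × 0.037 = 5.8, with range 157 × 0.024 = 3.8 to 157 × 0.058 = 9.1. That is about 6 (4-9).
   - Of 133: 133 × 0.037 = 4.9, with range 3.2 to 7.7. That is about 5 (3-8).

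3. *Effect on implant survival.* With f the share who exit, true loss is (1 − f) × 0.03 + f × q, while the retained subjects show 0.03. The overstatement of survival is therefore f × (q − 0.03). At f = 0.037:
   - q = 3%: 0.037 × 0 = 0 points
   - q = 10%: 0.037 × 0.07 = 0.3 points
   - q = 20%: 0.037 × 0.17 = 0.6 points

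   At the ends of the cited interval, q = 20% gives 0.024 × 0.17 = 0.4 and 0.058 × 0.17 = 1.0 points.

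4. *What unknown status does to the estimate.* Suppose 3 losses are seen and 5 of 133 subjects have left with implant status unknown (both counts assumed).
   - Exits dropped: 3/128 = 2.3% lost (exact 95% CI 0.5-6.7%)
   - All 5 implants survive: 3/133 = 2.3% (0.5-6.5%)
   - All 5 implants lost: 8/133 = 6.0% (2.6-11.5%)

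5. *Safety observation time.* Even spacing means each exit loses on average 2.5 of 5 years. The share lost is 0.037 × 2.5/5 = 1.9% (1.2-2.9% over the cited interval).

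**The case against.** The case on the other side is substantial, and most of it limits the point.

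- The rule is permissive. An investigator need not discontinue the subject.
- Prosthetic failure is wider than replacement. Under section 6.3.1.2, "loss of conometric retention between abutment and final cap" is a failure in itself, yet section 1.1 says the crown can be removed and reattached up to ten times. A re-seated crown needs no new abutment or cap, so that subject stays.
- Data up to and including the failure are recorded. Section 6.4.2 names loss of retention, abutment loss or fracture, and implant loss as device effects. Section 6.4.5 follows open events until they resolve or are explained, and the Safety set keeps every enrolled subject with any data.
- Nothing in the documents shows that an implant under a replaced component does worse. If loss is the same in both groups, the bias is zero.
- Following subjects only while the original device is in place is a recognisable approach, and implant survival carries no hypothesis test.

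All of this stands except that the last item does not close the gap. The plan does not restrict implant survival to time on the original components. Section 6.3.2.2 counts any removal after the restoration, for any cause, to five years. Follow-up of open events also does not capture events that begin after exit.

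A reader might infer that implant survival and safety are observed only where the prosthesis did not fail, or that the long-term safety record lacks subjects with device failure. The first four items show why the documents do not support either reading. A reader might also compound the 97% one-year rate to 157 × (1 − 0.97⁵) = 22 exits. That implies 85.9% survival at five years, far below the interval of 94.2-97.6% that the plan cites for that time.

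**Conclusion.** The point holds in a limited form. Where the discontinuation option is used, implant status and new-onset adverse events are unobserved after an abutment or cap replacement, and no stated rule says how these subjects enter the five-year implant analysis. At the cited survival rate this concerns at most about 6 of 157 subjects, or 5 of 133, and about 2% of safety observation time. Implant survival would be overstated by 0 to about 0.6 points under the assumed loss rates.

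The counts treat every failure as a replacement and exit, which errs high. They also rest on a literature rate for implant-supported single crowns. The loss rates and even spacing of exits are assumptions. The direction of bias cannot be checked from the planned data, because the outcome after exit is what is missing. The primary analysis and the sample size are untouched. The change is worth making because it is cheap and the missing data may not be recoverable later.

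**What to change.** - In sections 5.5.1 and 5.5.2, record replacement of the abutment or final cap as a prosthetic failure on its date, and keep the subject in the scheduled visits for implant status and AE/ADE up to Visit 11 unless consent is withdrawn. Clinical care after replacement remains with the investigator; only data collection changes.
- In section 10.3.2, count these subjects in the implant survival denominator, and give best-case and worst-case bounds wherever implant status is unknown, as in step 4 of the working.

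The cost is an amendment and reimbursement of the remaining routine visits for about 5-6 subjects. No new procedure is needed. The sponsor may also see a slightly less favourable implant survival figure, if implants do worse after replacement.
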